4.7.1 Events of Special Interest

The following events of special interest will be monitored and may trigger an IDMC meeting, as well as may trigger study treatment interruption.

Abnormal liver function test results:

- ALT or AST >8x ULN
- ALT or AST >5x ULN for more than 2 weeks
- ALT or AST >3x ULN and (total bilirubin >2x ULN or International Normalized Ratio [INR] >1.5)
- ALT or AST >3x ULN with the appearance of worsening of fatigue, nausea, vomiting, right upper quadrant pain or tenderness, fever, rash, or eosinophilia
- Any other safety signals observed during routine data review that warrant convening of the IDMC, in the opinion of the Medical Monitor

Special ocular events:

- Ocular inflammation, including iritis and uveitis
- ≥ 2 grade increase in corneal edema, corneal staining or edema
- ≥ 2 grade increase in any cataract
- IOP change of ± 7 mmHg from baseline
- Loss of 15 letters or more BCVA

For each type of AE reported, the number and percent of participants will be tabulated based on the preferred term. The tables will be generated by relationship to treatment as well as by system organ class and severity, for treatment-emergent AEs, as well as pre-treatment AEs (occurring prior to first dose) and post-treatment AEs (occurring 3 days after the last dose).

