## 2.3 RISK/BENEFIT ASSESSMENT

### 2.3.1 KNOWN POTENTIAL RISKS

Risks of long-term (52-week) orally dosed nintedanib are described in the Ofev package insert and summarized in the AG-86893 Investigator's Brochure [28]. In brief, there was a dose-dependent increase in liver enzyme levels in patients. Liver enzyme increases were reversible with dose modification or discontinuation and were not associated with clinical signs or symptoms of liver injury. The most common side effects were gastrointestinal irritation (diarrhea, nausea, abdominal pain, vomiting, and decreased appetite), headache, weight decrease, and hypertension [33]. As with most anti-VEGF therapies, arterial thromboembolic events have been reported.

For AG-86893, the risk to the participant is expected to be low. In this study, the highest proposed dose of 0.3% given TID will expose participants to 0.36 mg of nintedanib per day (3 mg/mL x 0.040 mL x 3), which is over 800 times less than what has been approved for the RLD (300 mg; 150 mg

BID). Furthermore, the duration of treatment (28 days) is similar to the above Phase 1 study, in which no dose-limiting toxicities were observed at the 150 mg BID dose [27].

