#### 8.3.11 EVENTS OF SPECIAL INTEREST

Based on the observed reversible liver enzyme increases in animal models and humans in a clinical setting using the oral formulation nintedanib, abnormal liver function test results meeting the criteria below will be monitored and may trigger a meeting of the Independent Data Monitoring Committee (IDMC):

- ALT or AST >8x ULN
- ALT or AST >5x ULN for more than 2 weeks
- ALT or AST >3x ULN and (total bilirubin >2x ULN or International Normalized Ratio [INR] >1.5)
- ALT or AST >3x ULN with the appearance of worsening of fatigue, nausea, vomiting, right upper quadrant pain or tenderness, fever, rash, or eosinophilia
- Any other safety signals observed during routine data review that warrant convening of the IDMC, in the opinion of the Medical Monitor

Any of these parameters also represent a trigger for interruption of dose for the participant until the IDMC has been convened and a recommendation provided.

In the event of an increase in serum AST or ALT to >3x ULN, the following monitoring will be required:

- Repeat testing within 48 to 72 hours of ALT, AST, ALP, and total bilirubin to confirm the abnormalities and to determine if they are increasing or decreasing
- Participants will be questioned on the presence of symptoms (eg appearance of worsening of fatigue, nausea, vomiting, right upper quadrant pain or tenderness, fever, rash, or eosinophilia)

- If symptoms persist or repeat testing shows ALT/AST >3x ULN for the participants with normal baseline measures or 2-fold increases above baseline values for participants with elevated values before drug exposure, the following measures will be initiated to determine whether the abnormalities are improving or worsening:
  - Interrupt study treatment dosing until advice from the Medical Monitor is provided
  - Repeat liver tests (ALT, AST, ALP, and total bilirubin) 2 or 3 times weekly. Frequency of testing can decrease to once a week or less if abnormalities stabilize or study drug has been discontinued and participant is asymptomatic
  - Obtain a more detailed history of symptoms and prior or concurrent diseases
  - Obtain a history of concomitant drug use (including nonprescription medications, herbal and dietary supplement preparations), alcohol use, recreational drug use, and special diets
  - Obtain a history of exposure to environmental chemical agents
  - Obtain additional tests to evaluate liver function, as appropriate (e.g., INR)

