  - Consider gastroenterology or hepatology consultation

Ocular AEs of special interest include the following and will also be monitored by the Medical Monitor and the IDMC:

- Ocular inflammation, including iritis and uveitis
- $\geq 2$  grade increase in corneal edema, corneal staining or edema
- $\geq 2$  grade increase in any cataract
- IOP change of  $\pm 7$  mmHg from baseline
- Loss of 15 letters or more BCVA

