6.6.1 Adverse Events

All AEs reported during the study period will be recorded and coded using MedDRA terminology (MedDRA V21.0 at time of SAP publication, or the current version when superseded). An AE will be considered as treatment-emergent adverse event (TEAE) if it has an onset during the treatment period. A pre-existing event that worsens after the first dose date and within 3 days after the last dose date is considered a treatment emergent event.

The incidence of all TEAEs will be summarized using system organ class and preferred term by treatment group and overall. Adverse events will also be presented by relationship and severity. Further, serious adverse events and those events leading to discontinuation will also be presented.

Participants may have more than one AE per system organ class and preferred term. At each level of participant summarization, a participant will be counted once if they reported 1 or more events and will be reported with the highest severity. In cases where severity or relationship is missing, the most conservative approach will be taken (i.e. highest severity and assumed to be related).

The following overall summary will be presented by treatment and overall:

- Total number and percent of participants with
 - All AEs
 - Mild AEs
 - Moderate AEs
 - Severe AEs
 - Not related AE
 - Related AE
 - AE leading to death
 - AE leading to treatment discontinuation

- Total number and percent of participants with SAE
 - Mild SAE
 - Moderate SAE
 - Severe SAE
 - Not related SAE
 - Related SAE
 - SAE leading to Death
 - SAE leading to treatment discontinuation

The following summary tables of AEs will be presented by treatment and overall:

- Total number and percent of participants with AEs
 - By system organ and preferred term
 - By frequency for SAEs

- Total number and percent of participants treatment-related AEs
 - By preferred term and severity

The number and percent of participants with significant vital sign and laboratory findings during study will be summarized by group and overall.

The number and percent of participants with the following special interest events will be summarized by group and overall.

- Abnormal liver function (as defined in section 4.7.1)
- Ocular events

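### SAP 6.6.1 defines its liver-function count by a list in SAP 4.7.1 that ends in a Medical Monitor catch-all with no liver condition

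*SAP*

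**What the plan says.** SAP 6.6.1 commits to a table of special interest events: "The number and percent of participants with the following special interest events will be summarized by group and overall". It names two items. The first is "Abnormal liver function (as defined in section 4.7.1"; the second is ocular events. The pointer to 4.7.1 leaves out no part of the list it refers to.

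SAP 4.7.1 opens by saying that the events are monitored and may lead to an IDMC meeting or to interruption of treatment. Under its liver heading are five bullets. Four set ALT/AST thresholds. The fifth reads "Any other safety signals observed during routine data review that warrant convening of the IDMC, in the opinion of the Medical Monitor". The ocular list follows under a separate heading.

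Protocol 8.3.11 has the same five bullets and gives the reason for the category: "Based on the observed reversible liver enzyme increases in animal models and humans in a clinical setting using the oral formulation nintedanib". There the bullets define what may trigger an IDMC meeting and what interrupts dosing for the participant.

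**The concern.** A list written to decide when to call a committee has been reused as the definition of a count. The two uses need different things. A trigger list should end with a clause that lets the Medical Monitor act on anything unforeseen. A counting definition needs criteria that belong under the row's label and can be applied to each participant from recorded data. The fifth bullet meets neither need. A signal of any kind, an ECG finding for example, could satisfy it, and the participant would then be reported as having abnormal liver function.

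At stake is the one row that addresses the known systemic risk of the active ingredient. Protocol 2.3.1 puts the highest daily dose at "over 800 times less than what has been approved for the RLD", so true liver cases may well be few. In a row that would otherwise be empty, one misfiled participant would be the whole result.

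**Working it through.** The plan states no figure for this row, so there is nothing to reproduce. The check is a comparison of text, followed by simple arithmetic for scale.

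**Text.** The five bullets under the liver heading of SAP 4.7.1:

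1. ALT or AST above 8 times ULN: a liver condition, with a threshold.
2. ALT or AST above 5 times ULN lasting over 2 weeks: a liver condition, with a threshold and a duration.
3. ALT or AST above 3 times ULN, with raised bilirubin (above 2 times ULN) or INR (above 1.5): a liver condition, with thresholds.
4. ALT or AST above 3 times ULN with listed symptoms or eosinophilia: a liver condition, with a threshold.
5. The catch-all: no ALT, AST, bilirubin, INR or other liver term, and no threshold. It depends on the Medical Monitor's opinion.

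SAP 6.6.1 takes its definition from the section as a whole. No other text in the SAP or protocol limits the pointer to bullets 1 to 4, and no other row in SAP 6.6.1 is set aside for events that meet only bullet 5.

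**Scale.** Inputs: about 70 participants enrolled and about 20 evaluable per group (Protocol 9.2, SAP 3.3), and 1:1:1 allocation. The safety population is all randomized participants with at least one dose (SAP 5.2), so the enrolled number is the better denominator.

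- Arm size: 70/3 = 23.3, taken as 23.
- One participant counted through bullet 5 alone: 1/23 = 4.3 percentage points. With 20 per arm it would be 1/20 = 5.0 points.
- In the overall column: 1/70 = 1.4 points.
- Exact (Clopper-Pearson) 95% interval for 0 of 23: 0 to 1 − 0.025^(1/23), that is 0 to 14.8%.
- Exact 95% interval for 1 of 23: lower limit 1 − 0.975^(1/23) = 0.1%; the upper limit solves (1−p)^23 + 23p(1−p)^22 = 0.025, which gives 21.9%.
- Dose comparison: 300 mg / 0.36 mg = 833, in line with the protocol's statement.

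The step from 0 of 23 to 1 of 23 shows what one miscount would do. It is not evidence that a miscount would occur.

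**The case against.** The strongest reply is that the surrounding text already limits the bullet. It sits under a heading about liver function tests, the row is labelled as liver function, and the protocol's lead-in speaks of liver test results. A sensible programmer would derive the row from ALT and AST and ignore an opinion that no described data field records. This makes an actual miscount less likely. It does not make the definition right. The bullet speaks of any other safety signal, and even if the heading confined it to the liver it would still have no threshold to apply. Leaving it out would be an unwritten departure from a written rule. SAP 9 requires two independently programmed datasets to match exactly, so the text should settle the point.

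The second reply is that other outputs would expose a miscount. SAP 4.7.1 provides that "For each type of AE reported, the number and percent of participants will be tabulated based on the preferred term", SAP 6.6.1 also counts significant laboratory findings and lists adverse events by participant, and Protocol 9.4.8 promises line listings. This stands. With about 23 per arm a reader could trace a single case. The IDMC is convened by the Medical Monitor as findings arise (Protocol 10.1.6), not from this table.

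The third reply is that SAP Module II, with the table shells, may already show only the four ALT/AST criteria. That is possible and cannot be checked here.

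A reader might also infer that the ocular row has the same fault, because its criteria are unlike one another and include "IOP change of ± 7 mmHg from baseline". The documents do not support that. All five criteria are ocular, so none falls outside its label. The SAP names the category without saying that the criteria will be pooled, and Module II may set out the display. How those rows are laid out is a matter of presentation.

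**Conclusion.** The counting rule in SAP 6.6.1 is wrong as written: taken literally, it admits non-liver signals to the liver row. The wording is certain. Whether the final table would be wrong is not, because that depends on how often the Medical Monitor uses the catch-all, on how the programmers read the pointer, and on Module II.

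The consequence is minor. The row is descriptive, and the primary endpoint and its error rate are untouched. Each miscounted participant would move an arm's rate by about 4.3 points, assuming 23 per arm.

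Two stronger readings are tempting and do not hold. One is that the row would be biased between arms; nothing in the documents suggests that the catch-all would be used more in one arm than another. The other is that Protocol 8.3.11 is itself at fault. There the catch-all does its proper job as a trigger, and the problem arises only when SAP 6.6.1 borrows the list as a definition.

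**What to change.** Change SAP 6.6.1 only. Define the liver row as any of the four ALT/AST criteria in section 4.7.1. Add a separate row, labelled other IDMC trigger, for any event that qualifies only through the Medical Monitor's judgement, so that no safety event disappears from the table. If the Module II shells already restrict the liver row in this way, bring the SAP 6.6.1 wording into line with them and check that the other triggers still have a row.

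Leave Protocol 8.3.11 unchanged. Its scope for IDMC meetings and dose interruption is then unaffected, and no protocol amendment is needed.

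The cost is one line of SAP wording and one added table row, with no new data. The only drawback is that events are spread over two rows, each with a smaller count.

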5 ANALYSIS POPULATIONS

Five analysis populations will be defined and used in the statistical analyses: (1) intent-to-treat population, (2) safety population, (3) modified intent-to-treat (mITT) population, (4) per-protocol (PP) population, and (5) if available, PK sub-study population for PK analysis.

5.1 Intent-to-treat population

The intent-to-treat population will include all participants who signed an informed consent for study participation and has received a randomization assignment.

5.2 Safety Population

The safety population will include all randomized participants who receive at least one (1) dose of study eye drop. Results will be presented based on the treatment actually received. All safety analyses will be conducted using the safety population.

5.3 Modified Intent-to-Treat Population

The modified intent-to-treat (mITT) population will include all randomized participants who receive at least one dose of study eye drop and had conjunctival hyperemia evaluated at both the Day 1 and Day 28 visits. This is the efficacy population. Results will be presented by the treatment assigned during randomization.

The primary efficacy analyses will be conducted using the mITT population.

5.4 Per Protocol Population

The per-protocol (PP) population will consist of all participants in the mITT population who do not have major protocol deviations considered to affect the primary efficacy variable, have been at least 70% compliant with the study treatment according to participant dosing diary AND have been administered IP according to protocol at least 4 of the 6 doses immediately prior to that study visit.

The rules for determining exclusion from the per-protocol population will be made and implemented prior to database lock.

Sensitivity analyses of the primary efficacy analyses will be conducted using the PP population.

5.5 Pharmacokinetic Sub-Study Population (If available)

The Pharmacokinetic (PK) sub-study population, if available, will consist of participants who participate in the PK sub-study and have all blood samples available for PK analysis. Results will be presented by the treatment actually received.

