- i) At selected sites, blood (~10 mL) for plasma drug monitoring will be collected on Day 1 and Day 28 pre-dose and post-dose at 0.5 and 1 hour after the morning dose; on Day 56, a single sample will be collected
- j) On Day 1, study drug will be dispensed and the first dose will be administered in the clinic after all study-related procedures have been performed. On Day 28 (the last day of treatment), the morning dose will be administered in the clinic prior to all study-related procedures, except the participant questionnaire
- k) Height and weight at screening; weight only at other timepoints
- l) Participants will be questioned on AEs approximately 1 hour after IP administration

Additional examinations and unscheduled visits can be included as safety concerns arise.

AE, adverse event; AS-OCT, anterior-segment optical coherence tomography; BCVA, best-corrected visual acuity; ECG, electrocardiogram; IOP, intraocular pressure; OU, both eyes; SE, study eye; TFBUT, tear film break-up time.

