- **Plasma drug monitoring.** In a subset of at least 6 participants per study group (at select study sites), blood samples (~10 mL per sample) will be collected for monitoring the plasma concentrations of AG-86893 on Day 1 and Day 28 at pre-dose and at 0.5 and 1 hour after the morning dose from participating participants. At Day 56, a single blood sample will be collected at the study visit. Plasma drug concentrations will be measured using a validated liquid chromatography, tandem mass spectrometry assay, with a target lower limit of quantitation of 0.020 ng/mL. Allgenesis shall have full ownership rights to any biological samples derived from the study.

Unscheduled visits can be included if safety concerns arise. Additional examinations may be performed as necessary to ensure the safety and wellbeing of participants during the study. Electronic Case Report Forms should be completed for each unscheduled visit.

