3.1.5 Pharmacokinetic Measure (if applicable)

A subset of 6 participants from each treatment group will participate in a PK study to collect blood samples on the morning of Day 1 and Day 28 at pre-dose, at 0.5, 1 hour post-dose. On Day 56, a single blood sample will be collected. Plasma drug concentrations will be measured using a validated liquid

chromatography, tandem mass spectrometry assay, with a target lower limit of quantitation of 0.020 ng/mL.

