6.7 Pharmacokinetic Analyses (if data available)

Pharmacokinetic analysis, if applicable, will be based on the PK sub-population using a model-independent approach.

Drug plasma concentration data will be summarized for each dose by descriptive statistics using SAS®. AUC_{0-1h} will be estimated using linear trapezoidal method.

Individual and mean concentration at each time point, C_{max} , T_{max} , and AUC_{0-1h} , where applicable, will be presented by treatment group for Day 1 and Day 28. On Day 56 individual and mean \pm SD will be presented.

Individual and mean concentration-time curves will be presented for Day 1, and Day 28 to illustrate the dynamic change of plasma concentration from hour 0 to 1.

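### The PK population requires every scheduled blood sample, so a single missed draw removes a participant's other valid concentrations from the summaries, and the SAP does not say what "all" means at the first database lock

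*SAP*

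**What the plan says.** SAP 5.5 defines the PK population as those who take part in the sub-study and "have all blood samples available for PK analysis". SAP 6.7 then says that the analysis "will be based on the PK sub-population using a model-independent approach". Neither section has a rule by day, time point or parameter.

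The draws are set out in SAP 3.1.5. Blood is taken "on the morning of Day 1 and Day 28 at pre-dose, at 0.5, 1 hour post-dose", and then "On Day 56, a single blood sample will be collected". Protocol 1.3 (footnote i) and Protocol 8.2 give the same schedule.

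On size, SAP 3.1.5 says "A subset of 6 participants from each treatment group will participate in a PK study". Protocol 8.2 sets a floor instead: "In a subset of at least 6 participants per study group (at select study sites").

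SAP 8 plans two locks. The first comes once all participants have completed Day 28 and includes the PK analysis if applicable. The second comes at study completion. Eligibility for analysis is settled before each lock.

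Protocol 9.4.10 summarises Day 1 and Day 28 concentrations and derives parameters whenever possible. It contains no complete-sample requirement.

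**The concern.** The rule is stricter than any summary it serves. SAP 6.7 reports Cmax, Tmax and AUC0-1h for Day 1 and Day 28 only, and each uses that day's three samples. A Day 1 profile does not depend on Day 28, and neither depends on Day 56. Requiring all seven draws therefore lets a missed sample remove data to which it contributes nothing.

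One exclusion is built in. Under Protocol 7.1 and SAP 6.2.3, stopping study drug means leaving the study. A participant who stops before Day 28 cannot complete the set, so their Day 1 concentrations leave the summaries. If stopping is related to tolerability, the exposure summary omits people for whom exposure is of particular interest.

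Protocol 2.1 says that the pharmacokinetics have not been studied in humans after topical instillation, and plasma concentration is a stated objective. These few participants are this study's only source of that information.

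**Working it through.** **Number of draws.** From SAP 3.1.5: 3 (Day 1) + 3 (Day 28) + 1 (Day 56) = 7 per participant, or 6 × 7 = 42 per arm of 6. The 4-hour sample in the SAP 1.1 table of changes belongs to a summary of changes and is not counted.

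**Cost of one exclusion.** 1/6 = 16.7% of an arm at 6 per group. It is less if the protocol's minimum is exceeded.

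**The plan's own figure.** No formula lies behind the 6 per group, so there is none to reproduce.

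**Expected number retained.** The documents give no miss rate. The rates below are assumptions, shown under two patterns of loss. Let p be the chance of a miss.

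- Draws missed independently: P(complete) = (1 − p)^7.
- Whole visits missed (Day 1, Day 28, Day 56): P(complete) = (1 − p)^3.
- Expected retained of 6 = 6 × P(complete).

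| p | (1 − p)^7 | kept of 6 | (1 − p)^3 | kept of 6 |
|---|---|---|---|---|
| 2% | 0.868 | 5.21 | 0.941 | 5.65 |
| 5% | 0.698 | 4.19 | 0.857 | 5.14 |
| 10% | 0.478 | 2.87 | 0.729 | 4.37 |

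**Chance that an arm of 6 keeps 3 or fewer, at p = 5%.** Binomial with n = 6: 0.259 when P(complete) = 0.698, and 0.041 when P(complete) = 0.857. The result depends heavily on the pattern of loss.

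**Comparison with a per-day rule.** If only a day's own three samples are needed for that day's AUC0-1h, the number kept under independent misses is 6 × (1 − p)^3 = 5.65, 5.14 and 4.37. If whole visits are missed it is 6 × (1 − p) = 5.88, 5.70 and 5.40. Either way, more profiles are kept than under the all-seven rule.

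**Timing against SAP 8.** Two readings are open:

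- If "all" means all seven, anyone not yet at Day 56 is outside the PK population at the first lock, although a PK analysis is scheduled there.
- If "all" means all samples due by that lock, a participant with six of six at the first lock who then misses Day 56 is in the first PK analysis and out of the final one.

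The SAP does not choose between them.

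**Footnotes to Protocol 1.3.** Footnote i calls for a Day 28 pre-dose sample. Footnote j says that on Day 28 "the morning dose will be administered in the clinic prior to all study-related procedures, except the participant questionnaire". Taken together these conflict, because the pre-dose draw is not among the exceptions.

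**The case against.** A reader might infer that a missed Day 56 visit always deletes valid Day 1 and Day 28 profiles. The documents do not support that. SAP 8 places a PK analysis at the first lock and settles eligibility before each lock, so "all" can reasonably mean all samples due by then. The Day 56 effect is clear only at the final lock. This objection stands.

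It is also tempting to say that an arm has about a one-in-four chance of falling to 3 or fewer. That figure needs a 5% miss rate and seven independent misses. Draws cluster in three visits, and if whole visits are missed at 5% the chance is about 4%. Neither rate comes from the documents, and the protocol's 6 is a minimum. This stands too.

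Three further points stand in part:

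- The data would not vanish. Protocol 9.4.8 and SAP 7.4 and 7.5 provide individual listings, so the loss is from the summaries. PK is unpowered and conditional on data being available.
- A participant who stops before Day 28 has no Day 28 profile under any definition. Only the Day 1 data are at stake.
- One of the three arms is vehicle, where a lost participant costs nothing for drug exposure.

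Finally, footnote j need not cost any site its pre-dose sample. Footnote i, Protocol 8.2 and SAP 3.1.5 all specify that draw, and the Manual of Procedures is not available here. The conflict is in the text, and its effect in practice is unknown.

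None of this supplies a reason for the all-samples rule. The general statement in SAP 6 that missing data are handled as is does not readmit someone whom the population definition has excluded.

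**Conclusion.** The concern holds as a defect in the population definition. As written, SAP 5.5 and 6.7 drop valid concentrations from the PK summaries because of a missed draw that those summaries do not use. They drop the Day 1 data of anyone who stops before Day 28, and they leave eligibility undefined at the first lock. The two statements about early stopping and the first lock rest on the text alone and need no miss rate.

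Each exclusion costs up to one sixth of an arm. Across the assumed rates of 2% to 10%, the expected number kept of 6 runs from 5.2 down to 2.9 under independent misses, and from 5.6 down to 4.4 under whole-visit misses. Whole-visit loss is arguably closer to how draws are scheduled. These ranges take 6 per group and are illustrations, not forecasts.

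The consequence is confined to descriptive PK results and to whom they represent. The primary analysis is unaffected.

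**What to change.** Amend SAP 5.5, 6.7 and 8 as follows:

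- Define the PK population as sub-study participants who received study drug and have at least one post-dose sample with a reported assay result. State that a BLOQ (below the limit of quantification) result counts as a result. SAP 7.5 sets post-dose BLOQ values to missing for calculations. Without this statement, participants with the lowest exposure could drop out of the population and push mean exposure upward.
- Summarise each time point with all available values and show n.
- Derive AUC0-1h, Cmax and Tmax for any day on which that day's three samples were taken, and state how a BLOQ value enters each derivation.
- Apply the same rule at both locks.

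The cost is a short SAP revision before the first lock. The one small downside is that n varies by time point, which SAP 7.5 already allows in effect by setting BLOQ values to missing.

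Separately, footnotes i and j of Protocol 1.3 contradict each other on the order of the Day 28 pre-dose sample and the Day 28 dose, and must be reconciled.
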